OAS-M: The OAS-M is a 25-item clinician-administered, semi-structured interview with nine subscales^{45, 47}. It was designed to evaluate various manifestations of aggressive behaviors in outpatients, including the severity, type, and frequency of aggressive behavior. The scale assesses three overall domains: Aggression (Verbal Aggression, Aggression Against Objects, Aggression Against Others, and Aggression Against Self), Irritability (Global Irritability and Subjective Irritability), and Suicidality (Suicidal Tendencies, Intent of Attempt, and Lethality of Attempt). Only the Aggression and Irritability subscales will be used in the current study. The two Irritability subscales are rated on Likert-type scales from 0 = none at all to 5 = extreme. The Aggression scale uses a different format in which each specific behavior is scored separately by frequency and then multiplied by assigned weights. For each Aggression subscale, seven specific behaviors are listed in order of severity and then weighted by their respective rank. The weighted frequencies are summed to form each subscale score. Subscale scores are then multiplied by their own assigned weight: Verbal Aggression by 1, Aggression Against Objects by 2, and Aggression Against Others and Self each by 3. Weighted subscales are added to obtain a final scale score for Aggression. Evidence for inter-rater and test-retest reliability has been documented for the OAS-M, with intraclass correlations (ICCs) of .91 and greater for inter-rater, and ICCs of .46 to .54 for test-retest reliability, and the OAS-M has demonstrated sensitivity to pharmacotherapy-induced changes in aggression^{47, 48}. The time frame of the OAS-M is restricted to the past week. The OAS-M will be administered by interviewers blinded to treatment condition.

Anger Consequences Scale (ACQ): The ACQ is a brief self-report measure developed to assess the frequency of negative anger-related behavioral consequences. Internal consistencies of .75 to .91 were reported on the original 42 item version; the revised version shortened the measure to 33 items based on factor analysis⁴⁹. This scale includes items not covered by the other anger measures, including for example, trouble with the law, driving recklessly, getting into an accident, damaging relationships, etc.

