Treatment Satisfaction: a brief 4 item measure adapted from the Treatment Satisfaction Form used in the NIMH Treatment of Depression Collaborative Research Program will be used to assess satisfaction with treatment.

Treatment Utilization: The Longitudinal Interval Follow-Up Assessment (LIFE) treatment section provides continuous recording of mental health and medical treatments⁵². For the latter, number of hospitalizations, days spent in hospital, and number of outpatient visits for non-mental health medical treatments are recorded for the time period covered. Types and amounts of all mental health contacts, including inpatient and outpatient treatment, are recorded on a monthly basis. All psychiatric medications, including dosages are recorded on a weekly basis (see Appendix 4 for list of medications). We will also assess all prescribed non-psychiatric medications, over the counter medications (including caffeine), and herbal and other supplements taken for any reason.

A baseline version (LIFE-Base) assesses mental health treatment received prior to entering the study. We will adapt the LIFE-Base to indicate whether prior treatment occurred before, during, or after deployment, and also to assess whether prior treatment focused specifically on anger or PTSD.

D. 7. Schedule of Assessments

The schedule of assessments is shown in Table 1. The CAPS and the SCID will be administered during the screening process prior to randomization to ensure that only eligible participants are entered into the study. Only eligible participants will complete the full CAPS and SCID and other pre-treatment measures. Assessments will be conducted at pre-treatment, during treatment (after sessions 4 and 8), end of treatment (week 12), and at three and six months following completion of treatment. We estimate that completion of the SCID and the CAPS will take 2 hours on average, and that the remaining pre-treatment measures will take about 2 ½ hours. The pre-treatment assessment will be conducted in 2 sessions. Mid-treatment assessments should take about 45 minutes. We estimate that post-treatment and follow-up assessments will take about 2 ½ hours on average.

We will aim to complete the post-treatment and follow-up assessments in a single

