session, providing breaks if needed. If necessary due to participant burden, we will schedule a second assessment session. We will prioritize the order of measures administered to ensure that in all cases the anger outcome measures (OAS-M, STAXI-2, and ACQ), and the Outcomes Questionnaire are completed. Telephone assessments will be used if participants are unable to come in for assessments. Every attempt will be made to perform post-treatment and follow-up assessments within one week of their scheduled date.

Table 1. Schedule of Assessments

Domain	Screening	Pre-Tx	Sessions 4 and 8	Post-Tx	Follow-up (3 and 6 months)
Inclusion/exclusion Criteria					
SCID	X				
CAPS	X			X	X
Sample Characterization					
SNAP-2		X			
CTQ		X			
Combat Exposure		X			
BSI		X	X	X	X
BAM (Use subscale)		X			X
Anger					
OAS-M*		X	X	X	X
STAXI-2*		X	X	X	X
ACQ*		X		X	X
DAR (weekly)					
Function/QOL					
LIFE psychosoc		X		X	X
OQ		X		X	X
Disability Scale		X		X	X
WHOQOL-BREF		X		X	X
Mediators					
NAS arousal		X	X	X	
NAS cognitive		X	X	X	
NAS behavioral		X	X	X	
Other Measures					
Tx Satisfaction				X	
LIFE Tx section	X			X	X

Clinician administered interviews are in italics. ACQ = Anger Consequences Scale; BAM = Brief Addiction Monitor; BSI = Brief Symptom Inventory; CTQ = Childhood Trauma Questionnaire; DAR = Dimensions of Anger Scale; NAS = Novaco Anger Scale; OAS-M = Overt Aggression Scale Modified; OQ = Outcomes Questionnaire; SNAP-2 = Schedule for Nonadaptive and Adaptive Personality-2nd Edition; STAXI-2 = State Trait Anger Inventory-2; WHOQOL-BREF = The World Health Organization Quality of Life

*Collateral assessments will be administered at pre- and post-treatment

D. 8. *Blinding of Assessments*

All interviewers will be blind to participants' treatment condition. Each of the outcome domains (anger, functioning/quality of life) includes one blinded interview. Prior to the outcome assessments, the interviewer will remind each participant not to reveal his treatment condition. At the post-treatment and follow-up assessments, interviewers will complete questions including whether they think the blind was broken, and to which treatment condition they think the participant was assigned.

D. 9. *Standardization of Assessments*

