- Arousal reduction, including diaphragmatic breathing, and guided imagery training
- Cognitive restructuring of anger schemas (identification and modification of beliefs and interpretations)
- Behavioral coping strategies (training in communication, assertiveness, and strategic withdrawal)
- Inoculation training (practicing the cognitive, arousal regulatory, and behavioral coping skills while visualizing progressively more intense anger-arousing scenes from personal hierarchies).

E.3. Supportive Intervention Control

The Supportive Intervention adapted for the pilot study included the same “Battlemind” psychoeducation as the CBI condition. Following the psychoeducation component, the rest of the intervention focuses on providing support and using problem solving strategies to help in managing behavior and feelings in current day-to-day life. Cognitive behavioral interventions are excluded. In addition to the exclusion of cognitive or behavioral strategies, SI is less structured; the patient has more input into the agenda of the sessions.

E.4. Therapist Selection, Training and Supervision

Therapists will be Ph.D. level psychologists or masters level clinical social workers with prior experience in cognitive behavioral therapy and prior experience treating PTSD patients. Therapists will receive training in both interventions. There are advantages and disadvantages to using the same or different therapists for study conditions. The primary concern with using the same therapists is the possible effect of a different level of enthusiasm and investment in the active treatment condition, which can bias results. However, bias can just as easily occur when therapists are assigned to deliver different treatment conditions. Our experience in the pilot study was that therapists appeared to be equally comfortable with both conditions, and ratings indicated adherence to the manual. Retention was slightly higher in the SI condition. An advantage of using the same therapist for both conditions is reduction of between treatment variance associated with therapist effects. Another advantage is the increased flexibility of assigning study participants to therapists to facilitate accommodation of study participants’ availability for appointments.

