Assessments and intervention sessions will occur at the Providence VAMC. The veterans will be informed that their VA medical records will note their enrollment in a research study with a copy of their consent form attached. In addition, their attendance at each AE or HEC session will be noted in their medical records. This will include, if applicable, any safety issues (e.g., suicidal or homicidal statements they made) and how these were addressed in session. The veteran will be informed that none of the other data from this study will be included in their medical records, except for attendance at intervention sessions. All study data, stripped of identifying information, will be locked in a file cabinet as described above. Records will be maintained per Veterans Affairs Record Control Schedule 10-1.

6. Data Safety and Monitoring

Monitoring of safety in the proposed study will be the responsibility of all personnel on the project, with primary responsibility and supervision by [name]. The Institutional Review Board at the Providence VA Medical Center will approve the protocol and the

Statement of Informed Consent for the study and will provide oversight of data and safety issues.

Separate review of the protocol and consent form are made by the safety officer at the VA Medical Center. The study protocol will receive IRB approval prior to soliciting or requesting consent from any participants. Moreover, the study will be reviewed on an annual basis by the IRB committee with regard to recruitment and retention and annual reports will be made by the PI to the IRB chair of the Providence VA Medical Center regarding the progress of the proposed project, including any issues pertinent to recruitment, retention, confidentiality, and safety of human subjects. Any incidents that involve a breach of this plan or serious accident/injury will be reported to the IRB chair at the Providence VA Medical Center. As discussed, potential risks, albeit minimally likely, include distress or discomfort with questions regarding trauma history.

Adverse Event Reporting

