In the case of an Adverse Effect (AE) or a Serious Adverse Effect (SAE), a written report of the AE or SAE will be prepared for the Chair of the IRB at the Providence VA Medical Center. Any such AEs or SAEs will be presented to the full IRB committees. SAEs will be reported within 24 hours. Examples of serious adverse effects include death, life-threatening adverse events, suicide attempts, and inpatient hospitalization. The report of such AEs or SAEs will include whether they were expected or unexpected, a rating of severity of the event, a brief narrative summary of the event, a determination of whether a causal relationship existed between the study procedures and the event, whether the informed consent should be changed as a result of the event, and whether all enrolled participants should be notified of the event. The annual progress reports to the IRB require summary information regarding all AEs and SAEs occurring during that year. We have appointed [name] as our medical monitor. [name] is a Providence VA Medical Center physician and researcher who works independently from our research. He will be called upon to review all AEs and SAEs, and to provide input regarding the possible connection to the study protocol.

7. Risks / Benefits Assessment

A. Protection Against Risks

Potential risks include distress associated with discussing traumatic or other disturbing events or emotions, and breach of confidentiality.

Risk: Emotional distress associated with discussing traumatic or other upsetting events or emotions.

Minimization: Study participants will participate in assessments and treatment sessions during which they may identify and discuss difficulties they are having with anger and with their adjustment home from a hazardous deployment. They also may discuss upsetting events that they experienced while deployed. Although the assessments are

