unlikely to be more upsetting than standard clinical assessments, discussion of these experiences may make them feel uncomfortable. Should this happen, veterans will be informed that they can refuse to answer any question they wish or stop the interview at any time. Any participant verbalizing or showing signs of distress will be asked to remain in the assessment or treatment setting until their distress is at a manageable and comfortable level. No participant judged to be in danger of hurting him/herself or others will be allowed to leave the study setting unaccompanied. All study personnel who interact with study participants will have been professionally trained to respond to negative emotions if these should occur and to access emergency services if necessary.

Collateral participants will also be informed that they may refuse to answer any question or stop the interview at any time. It is unlikely, but possible, that a collateral participant may show signs of distress. The same procedures will apply to these participants, i.e. if distressed they will remain in the assessment setting until their distress is at a manageable level. [name] will be available by phone or in person to study personnel during assessment and treatment sessions. She will be contacted immediately if there are any concerns about the participant's emotional state, or upon any signs of suicidal or homicidal risk. All participants will be eligible for emergency services including referral to the Veterans Affairs Medical Center interim care during normal business hours or the emergency room after hours and on weekends and holidays, and inpatient hospitalization.

Additionally, therapists will be doctoral level psychologists or masters level social workers, and trained to help veterans reduce and manage feelings of intense anger. Assessments will be conducted by trained staff with prior experience in conducting clinical interviews in psychiatric samples. Veterans will have the opportunity to discuss any uncomfortable feelings with the assessment interviewers and treatment providers. The veteran will also be informed that the therapist and assessment interviewer will always place the veteran's well-being and safety over research considerations. Furthermore the veteran will be informed that should they experience any problems, they should report them to their therapist or to the principal investigator of this study.

Risk: Breach of Confidentiality

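### No active, arm-neutral adverse-event questioning is specified, scheduled interview answers are not linked to AE/SAE reporting, and no harms summary by arm is planned

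*Combined protocol and SAP*

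**What the plan says.** **Route by which harms reach the study.** Section 7.A, under minimization of emotional distress, tells veterans that "should they experience any problems, they should report them to their therapist or to the principal investigator of this study". It also expects staff to respond to visible distress, and to contact the responsible study lead on signs of suicidal or homicidal risk.

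**Reporting once an event is known.** Section 6, Adverse Event Reporting, begins from the case where an AE or SAE has occurred. It requires a written report to the IRB, a 24-hour limit for SAEs, an annual summary, and review of all AEs and SAEs by an independent medical monitor. "Examples of serious adverse effects include death, life-threatening adverse events, suicide attempts, and inpatient hospitalization". Earlier in section 6, "Any incidents that involve a breach of this plan or serious accident/injury will be reported to the IRB chair".

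**Scheduled questions on related events.**
- The LIFE treatment section (D.6) covers medical care: "number of hospitalizations, days spent in hospital, and number of outpatient visits for non-mental health medical treatments are recorded for the time period covered". For psychiatric care, "Types and amounts of all mental health contacts, including inpatient and outpatient treatment, are recorded on a monthly basis". In Table 1 the row "LIFE Tx section" is marked at screening, post-treatment and follow-up, but not at sessions 4 and 8.
- The OAS-M (D.2) asks about aggression against others and self at sessions 4 and 8, post-treatment, and 3 and 6 months. "The time frame of the OAS-M is restricted to the past week". Its suicidality subscales are not used.
- The ACQ (D.2) includes legal trouble and accidents, at pre-treatment, post-treatment, and 3 and 6 months. No look-back period is stated.

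**Arms.** On the pilot, E.4 notes: "Retention was slightly higher in the SI condition". No figure is given. G.2 describes no AE or SAE summary by arm.

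**The concern.** A harms record is comparable between arms only if both arms are asked the same question, at the same times, over the same period. Here the stated routes are participant report and staff observation, and the therapist is one of the two named recipients. Therapist contact stops when a participant leaves therapy, and at week 12 for everyone. If retention differs by arm, as it did slightly in the pilot, so can the chance that an event is recorded.

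The scheduled interviews could supply an arm-neutral record, but the plan treats them as outcome and utilization data. Nothing says that a hospitalization given in the LIFE, or a serious event disclosed in the OAS-M or ACQ, is compared with the AE/SAE log.

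At stake is whether the trial can describe harms by arm for a treatment that section 1 hopes to see used in VA hospitals nationwide, and whether the benefit-risk statement in section 7.B can be checked against the trial's own data. The efficacy analysis is not affected.

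**Working it through.** The plan states no event rate, AE count or capture figure, so there is nothing of its own to reproduce. The check is of text, with simple arithmetic on coverage.

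**Step 1. Is an adverse-event question scheduled?** Table 1 lists diagnostic, anger, functioning, mediator, satisfaction and treatment-use measures, and no AE row. Adverse Event Reporting in section 6 gives no elicitation question, form or collection window. Section 7.A supplies only the passive routes.

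**Step 2. What do the scheduled measures cover?**

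| Event | Scheduled source | Look-back | Link to AE/SAE report |
|---|---|---|---|
| Hospitalization | LIFE: post-treatment, 3 and 6 months | Whole interval | None stated |
| Violence to others | OAS-M: five post-baseline times | 1 week | None stated |
| Legal trouble, accidents | ACQ: post-treatment, 3 and 6 months | Not stated | None stated |
| Suicide attempt without admission | OAS-M aggression against self only | 1 week | None stated |

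**Step 3. OAS-M coverage.** Inputs: 12 weeks of treatment (D.7); follow-up to 6 months, taken as 26 weeks; five post-baseline administrations (Table 1); a 1-week look-back (D.2).
- Whole period: 12 + 26 = 38 weeks; 5 × 1 / 38 = 13.2%.
- After treatment: 2 × 1 / 26 = 7.7%.
- With 6 months taken as 24 weeks: 5/36 = 13.9% and 2/24 = 8.3%.

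So about 86% to 87% of the period lies outside the OAS-M look-back. This applies to the OAS-M alone. The LIFE covers the whole interval for hospitalization when the assessment is completed, and the ACQ may partly offset the gap for violence.

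**Step 4. Delay.** The first LIFE treatment interview after screening is at about week 12. An admission in week 2 that nobody volunteered would first be asked about some 12 − 2 = 10 weeks later. In follow-up the spacing is 26/2 = 13 weeks. The SAE limit is 24 hours; the protocol does not say whether it runs from the event or from staff awareness.

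**Step 5. Arm dependence.** If the true event rates are equal, the observed rate ratio is (capture proportion in CBI) / (capture proportion in SI). The documents give neither proportion and no attendance figures. The direction is plausible from E.4; the size cannot be derived.

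**Step 6. Incomplete assessments.** G.3 expects 80% follow-up: 0.20 × 120 = 24 participants may lack some scheduled answers, including the LIFE.

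**The case against.** The other side has real substance. A reader might infer that harms are recorded solely when volunteered or noticed. The documents do not support that: the LIFE, OAS-M and ACQ ask about related events on a fixed schedule in both arms, and D.3 adds a collateral aggression interview before and after treatment. Nor are events seen by the IRB alone, since an independent medical monitor reviews them all.

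A reader might also take the SAE list to exclude violence. It is a list of examples, and serious accident or injury is reportable separately. Silence on assault or arrest is a matter of wording.

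The attendance argument is limited too. G.2 commits to seeking assessments from people who stop therapy, D.10 provides five contact attempts and telephone follow-up, the principal investigator remains a route after week 12, and participants may raise concerns with interviewers. Moreover, OAS-M Aggression is a primary outcome, rated by blinded interviewers and compared by arm with two-tailed tests, so a mean worsening of aggression under CBI could be detected.

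All of this stands, and it narrows the point. It does not supply a standard AE question, a step from scheduled answers to the AE/SAE log, or a table of events by arm. A comparison of mean aggression scores is not a count of serious events.

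**Conclusion.** The point holds as a gap in ascertainment and reporting. The protocol specifies no active, arm-neutral collection of adverse events, does not connect scheduled answers to AE/SAE reporting, and plans no summary by arm. The clearest gaps are suicide attempts without admission and violence outside the OAS-M windows (about 13% coverage of about 38 weeks, assuming 6 months is 24 to 26 weeks). Late discovery of early admissions is a third.

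Two stronger readings should be resisted. One is that most serious events would be missed: no event rates are given, and hospitalization, a named SAE example, is asked about for the whole interval. The other is that CBI would look safer by a calculable amount: capture can differ by arm, but the only support is an unquantified remark on pilot retention.

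This is a cheap improvement worth making. It is not a flaw in the efficacy comparison.

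**What to change.** 1. At the assessments already scheduled (sessions 4 and 8, post-treatment, 3 and 6 months), have the blinded interviewer ask one standard adverse-event question covering the whole period since the last assessment. Ask it after the primary outcome measures. For participants who complete every assessment this covers all 38 weeks, subject to recall. It also cuts the longest wait during treatment from about 12 weeks to about 4, taking sessions 4 and 8 as weeks 4 and 8, as G.2 does.
2. Check LIFE hospitalizations, and any OAS-M or ACQ answer that indicates a serious event, against the AE/SAE log, and report any not yet reported.
3. Add to G.2 a descriptive table of AEs and SAEs by randomized arm for all randomized participants. Show the number interviewed per arm at each assessment, because the question cannot reach those who miss it.

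Optional wording: state whether serious assault on another person or a violence-related arrest is reportable.

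Cost: protocol text, one short form and one table; a few minutes per assessment; more events to report; and a small risk of unblinding talk, limited by asking last. No new visits or staff are needed.
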